9.1.2 Analysis of Primary Parameter

The primary efficacy parameter is the change from baseline to Week 8 in PARS severity. The PARS severity score for GAD is assessed for all symptoms identified in the generalized anxiety section of the PARS symptom checklist. The PARS severity score for GAD will be derived by summing 5 of 7 severity/impairment/interference items (2, 3, 5, 6, and 7). If any of the items is missing, the severity score will be considered missing.

The primary analysis will be performed using an MMRM with treatment group, age group strata (7-11 vs. 12-17 years), sex, pooled study center, visit, and treatment group-by-visit interaction as the fixed effects and the baseline value and baseline value-by-visit interaction as the covariates. An unstructured covariance matrix will be used to model the covariance of within-subject scores. The Kenward-Roger approximation (Kenward and Roger, 1997) will be used to estimate denominator degrees of freedom. If the model convergence for the unstructured covariance matrix fails, then the Fisher scoring

Page 25 of 53

algorithm will be used to provide better initial values of the covariance parameters. In the event that the model still does not converge after using those initial values, simplified covariance structures will be used to fit the model in the following order until the model converges: (1) ante-dependence, (2) heterogeneous autoregressive, (3) Toeplitz, and (4) compound symmetry. If a structured covariance is used, then a robust sandwich estimator will be used for estimating the variance of the treatment effect estimate.

This analysis will only use the observed cases of post-baseline scores without imputation of missing values. The significance test for the difference in means at Week 8 will be based on least squares (LS) means using a 2-sided α of 0.05. Differences between treatments at the other post-baseline visits will also be estimated based on LS means.

The primary analysis will treat measurements after study withdrawal as missing in the MMRM modeling, leading to an estimate of the treatment effect while on treatment. Two sensitivity analyses, last observation carried forward (LOCF) and pattern-mixture model, will be performed on the primary efficacy parameter to assess the impact of the missing at random assumption of MMRM.

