To examine the consistency of the primary efficacy results across study centers, the treatment differences versus placebo treatment groups (mean \pm SE) in the change from baseline to Week 8 in PARS severity score, both OC and LOCF, will be graphed by pooled study center.

The comparison of escitalopram vs. placebo will be performed to assess study assay sensitivity.

To assess the impact of COVID-19 on the primary efficacy parameter:

- The primary analysis will be repeated for subjects that were not significantly impacted by COVID-19 (Global COVID-19 Impact Assessment score of 4 or higher, regardless of direction of impact; see section 9.2.5).
- A sensitivity analysis will be conducted by treating remote visits as missing, and analyzing the remaining data using the primary MMRM model.
- A sensitivity analysis will be conducted by repeating the primary analysis and adding the following to the model: an indicator of whether data was collected before or on and after the start of the pandemic (17 March 2020) and the indicator by treatment interaction.
- A subgroup analysis will be conducted by repeating the primary analysis for randomized patients before or on and after the start of the COVID-19 pandemic (17 March 2020).

The subject-level PARS scores will be listed

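### The COVID-19 period model in SAP 9.1.2 estimates one pandemic shift shared by Weeks 2 and 8, so it misstates the Week 8 effect by period whenever the shift differs between the two visits

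*SAP*

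**What the plan says.** SAP 9.1.2 defines the target: "The primary efficacy parameter is the change from baseline to Week 8 in PARS severity". The primary MMRM gives each visit its own treatment effect, because it includes "visit, and treatment group-by-visit interaction as the fixed effects and the baseline value and baseline value-by-visit interaction as the covariates". The covariance is unstructured, and the test is a Week 8 contrast of least squares means at two-sided 0.05.

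A list of four analyses then follows under the purpose "To assess the impact of COVID-19 on the primary efficacy parameter". The third repeats the primary analysis and adds an indicator for data collected "before or on and after the start of the pandemic (17 March 2020) and the indicator by treatment interaction". The indicator follows the date of the rating, so it can change within a subject. No term crosses it with visit, and the SAP does not say which contrast from this model will be reported.

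The fourth analysis is a companion: "A subgroup analysis will be conducted by repeating the primary analysis for randomized patients before or on and after the start of the COVID-19 pandemic". It keeps the full primary model but splits subjects by date of randomization.

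The schedules in protocol 8.1.2 and SAP 3.2, and the visit lists in protocol 9.2, place post-baseline PARS only at Week 2 and at Week 8 or early withdrawal.

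**The concern.** The primary model lets the treatment effect differ between Weeks 2 and 8. The period model keeps that, but forces the pandemic change in the effect to be the same at both visits. The coefficient therefore answers whether there was a shift pooled over Weeks 2 and 8. The stated question is whether the Week 8 effect changed.

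There is reason to doubt equal shifts. Every subject takes the starting dose for the first two weeks, and the first escalation decision comes at the Week 2 visit (protocol 8.4.1), so the Week 2 rating precedes any escalation. If the drug effect grows between the visits, even a proportional pandemic loss gives a larger shift at Week 8 than at Week 2. A loss confined to Week 8 would be diluted by the Week 2 data, and a change confined to Week 2 would appear as a change at Week 8.

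At stake is how this one sensitivity analysis is read. It is the only one of the four whose periods are defined by when the data were collected.

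**Working it through.** **Inputs from the plan** (SAP 14.0, protocol 11.9): 128 per arm, difference 2.30, SD 5.79, correlation 0.7, dropout 14%, power 85%.

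**Reproducing the stated power.** For a two-visit MMRM, the effective n per arm is 1/(r²/n_W2 + (1−r²)/n_W8). With all dropout after Week 2, n_W8 = 128 × 0.86 = 110.1, so n_eff = 1/(0.49/128 + 0.51/110.1) = 118.2. Then 2.30/5.79 × √(118.2/2) = 3.05, and Φ(3.05 − 1.96) is about 86%. With half the dropout before Week 2 it is about 85%. The plan's figure reproduces.

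**Assumed inputs, which the documents do not give.** Of the subjects, 50% have both ratings before 17 March 2020, 10% have Week 2 before and Week 8 after, and 40% have both after. The SD is 5.79 at both visits, and all dropout falls between the visits. Baseline, age, sex and center terms are left out, as are early-withdrawal ratings that fall in other visit windows.

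**Models.** Let s2 and s8 be the true pandemic shifts in treatment effect at Weeks 2 and 8.
- SAP model: effect at visit v = β_v + γ × period.
- Visit-specific model: effect at visit v = β_v + γ_v × period.

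Generalized least squares with these inputs gives, for the SAP model:
- fitted shift = 0.52 × s2 + 0.48 × s8, with SE 1.16 (1.33 for the visit-specific Week 8 shift);
- fitted Week 8 effect before = truth + 0.26 × (s8 − s2);
- fitted Week 8 effect during = truth − 0.26 × (s8 − s2).

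Power is Φ(|shift|/SE − 1.96) + Φ(−|shift|/SE − 1.96).

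*Worked case.* The Week 2 effect is 1.0 throughout, and the Week 8 effect is 2.30 before and 0 during, so s2 = 0 and s8 = −2.30. Fitted before: 2.30 − 0.26 × 2.30 = 1.70. Fitted during: 0 + 0.60 = 0.60. The shift is −1.10, and 1.10/1.16 = 0.95 gives power 16%. The visit-specific model has 2.30/1.33 = 1.73 and power 41%.

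| Week 2 effect, before → during | Week 8 effect, before → during | SAP model, fitted Week 8 before / during | Rejection, SAP model | Rejection, visit-specific |
|---|---|---|---|---|
| 1.0 → 1.0 | 2.30 → 0 | 1.70 / 0.60 | 16% | 41% |
| 1.0 → 0 | 2.30 → 0 | 1.96 / 0.34 | 29% | 41% |
| 1.0 → 0.5 | 2.30 → 1.15 | 2.13 / 1.32 | 11% | 14% |
| 1.5 → 0 | 2.30 → 2.30 | 2.69 / 1.91 | 10% | 5% |
| shift −2.30 at both visits | 2.30 → 0 | 2.30 / 0 | 51% | 41% |

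The visit-specific model recovers the assumed Week 8 effects in every row.

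**Sensitivity of the first row.**
- With 30% wholly pre-pandemic, power is 12% against 36%; with 70%, 19% against 37%.
- With a 50/50 split and no crossing subjects, the fit is 1.66 and 0.64, with power 12% against 33%.
- With a Week 2 SD of 4.0 in place of 5.79, the fit is 1.29 and 1.01 with 6% power. If also nobody crosses and the split is 50/50, it is 1.14 and 1.16, so the loss disappears.

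Simulation with estimated covariance, 1,500 trials per case, agrees: 0.17 against 0.40 for the first row, and 0.053 against 0.049 when nothing changes at either visit.

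**The case against.** Four points can be made for the plan, and each has some force.

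First, the model is not always wrong. With equal shifts, including none, it is unbiased and more precise, with SE 1.16 against 1.33 and power 51% against 41% for a shift of −2.30 at both visits. This stands, so the criticism is conditional on unequal shifts.

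Second, a loss at Week 8 with no change at Week 2 is the unfavourable case. Halving both effects leaves almost no difference in power. The documents also do not say that little effect is expected at Week 2; protocol section 6 puts steady state within about one week. This stands, and the whole range has to be shown.

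Third, the fourth analysis already gives unconstrained Week 8 effects. For subjects randomized on or after the date it would return the true 0 in the worked case. However, subjects randomized in the 8 weeks before the date count as before, although their scheduled Week 8 ratings fall in the pandemic. Adding the 10% who cross gives 2.30 × 50/60 = 1.92 for that group. With steady recruitment, subjects randomized in the last two weeks add about 3.3%, giving 2.30 × 50/63.3 = 1.82. The gap is only partly filled.

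Fourth, the SAP promises neither a significance test of the interaction nor period-specific Week 8 effects from this model. That is correct. What can be said is that the reported contrast is unspecified, and that any Week 8 contrast drawn from the model carries the constraint.

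**Conclusion.** The point holds in conditional form. As written, the third COVID-19 analysis estimates one shift common to Weeks 2 and 8, and it misstates the Week 8 effect by period whenever the two shifts differ. With the assumed split and equal SDs, the error in each period is about a quarter of the difference between the shifts: 0.60 points when 2.30 is lost at Week 8 only, 0.34 when both effects vanish, 0.17 when both are halved, and none when the shifts are equal. A smaller Week 2 SD makes it worse. The period split, the crossing share, the Week 2 effect and the shifts are all assumptions.

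A reader might infer that the plan as a whole would miss a pandemic loss of effect, or would report a benefit during the pandemic that is not there. The documents do not support that, because this is one of four COVID-19 analyses and the fourth is free of the constraint. Nor is the primary conclusion at risk: the primary test, its alpha and the 85% power do not depend on this model. It is a worthwhile, low-cost correction to a sensitivity analysis.

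**What to change.** In the third COVID-19 bullet of SAP 9.1.2, add indicator-by-visit and indicator-by-treatment-by-visit to the model. State that the output is the Week 8 treatment difference in each period and the difference between them, each with a 95% confidence interval.

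Present these as estimates. Even with the added terms, power is only about 33% to 41% for complete loss of the Week 8 effect in the splits above, and the interval for the between-period difference has a half-width of about 1.96 × 1.33 = 2.6 points, wider than the planned effect. A non-significant interaction should not be read as evidence that the pandemic had no influence.

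The cost is one SAP sentence and, with two scheduled post-baseline visits, two more fixed-effect parameters. The downside is some precision (SE 1.33 in place of 1.16) if the shift really is equal at both visits. No data collection changes.

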9.2 SECONDARY EFFICACY PARAMETERS

The secondary efficacy endpoints are as follows:

- Response rate on the PARS at acute treatment endpoint (Week 8)
- Remission rate on the PARS at acute treatment endpoint (Week 8)
- Change on the CGI-S from baseline to acute treatment endpoint (Week 8)
- Remission rate on CGI-S at acute treatment endpoint (Week 8)
- Change on the CGAS from baseline to acute treatment endpoint (Week 8)
- Remission rate on the CGAS at acute treatment endpoint (Week 8)
- COVID-19 impact assessment score at each visit.

Page 27 of 53

Inferential testing for the secondary endpoints will be reported with nominal p-values. No adjustments for multiplicity will be made. All confidence intervals will be 2-sided 95% confidence intervals, unless stated otherwise

9.2.1 Analysis of Response Rate on PARS

The response rate on the PARS at acute treatment endpoint (Week 8) is defined as 50% reduction on PARS severity score for GAD (using 5 PARS items: 2, 3, 5, 6, and 7) from baseline. The response rate of the PARS will be analyzed using a repeated measures model for categorical outcomes. Modeling will be completed using a categorical MMRM (MMRM-CAT) approach, in which a pseudo-likelihood-based repeated measures analysis will be used and implemented in SAS procedure GLIMMIX. A binary distribution with logit link will be used for the dependent variable. Classification variables for treatment, age group, sex, visit (as a categorical variable), treatment-by-age group interaction, treatment-by-sex interaction, treatment by visit interaction, treatment-by-age group-by-sex interaction, and baseline score as a covariate will be considered in the modeling. If the GLMM does not converge, a logistic regression model with treatment group and baseline score as explanatory variables will be used. For the logistic regression analysis, postbaseline missing data will be imputed using the LOCF approach.

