11.5.1.2 Secondary Efficacy Parameters

Inferential testing for the secondary endpoints will be reported with nominal p-values. No adjustments for multiplicity will be made. All confidence intervals will be 2-sided 95% confidence intervals, unless stated otherwise.

The secondary efficacy endpoints are as follows:

- Response rate on the PARS at acute treatment endpoint (Week 8)
 - Response is defined as a 50% improvement on the PARS severity score for GAD.
- Remission rate on the PARS at acute treatment endpoint (Week 8)
 - Remission is defined as PARS severity score for GAD ≤ 8 (using 6 PARS items: 2, 3, 4, 5, 6, and 7)
- Change on the CGI-S from baseline to acute treatment endpoint (Week 8)

CONFIDENTIAL

- Remission rate on CGI-S at acute treatment endpoint (Week 8).
Remission rate is defined as the percentage of subjects having a CGI-S score ≤ 2 at endpoint.
- Change on the CGAS from baseline to acute treatment endpoint (Week 8)
 - Remission rate on the CGAS at acute treatment endpoint (Week 8).
Functional remission is defined as CGAS > 70 .
- COVID-19 impact assessment score at each visit.

The response rate of the PARS will be analyzed using a repeated measures model for categorical outcomes. Modeling will be completed using a categorical MMRM (MMRM-CAT) approach, in which a pseudo-likelihood-based repeated measures analysis will be used and implemented in SAS procedure GLIMMIX. A binary distribution with logit link will be used for the dependent variable. Classification variables for treatment, age group, sex, visit (as a categorical variable), treatment-by-age group interaction, treatment-by-sex interaction, treatment-by-visit interaction, and treatment-by-age group-by-sex interaction, and baseline score as a covariate will be considered in the modeling.

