13.0 BLINDED INTERIM ANALYSIS

A blinded interim analysis will be conducted when approximately 75% of randomized subjects have either completed the study or discontinued from the study. The blinded interim analysis is to obtain an estimate of the pooled standard deviation of the change from baseline in the PARS score to Week 8 of the double-blind acute treatment period. The sample size will be re-estimated using simulation in the same manner as the original sample size as described in Section 14 using the estimated pooled standard deviation and dropout rate from the blinded interim analysis. If the estimated pooled standard deviation is larger than the assumed pooled standard deviation due to assumption deviation as well as COVID-19 remote visits or dropout rate is increased, the sample size in placebo and escitalopram treatment groups may be increased to ensure an adequate power. However, due to the difficulties in recruiting pediatric subjects with GAD, the number of subjects in each treatment arm will be capped at 160.

As the sample size re-estimation requires only the pooled standard deviation and dropout rate to be updated, all data and personnel will remain blinded for the interim analysis. Randomization code will not be released for the sample size re-estimation. There are no potential unblinding issues in the sample size re-estimation. As this is a blinded re-estimation, there is no impact on the overall Type I error rate of the study.

SAP SCT-MD-60 Allergan

Page 40 of 53

14.0 DETERMINATION OF SAMPLE SIZE

The sample size estimate was constructed using a simulation approach as described in Lu K. (2012).

The primary efficacy parameter is the change from baseline to Week 8 of the double-blind acute treatment period in PARS total score. To detect an effect size (treatment group difference of 2.30 units relative to pooled standard deviation of 5.79) of 0.39, a sample size of 128 subjects in the escitalopram treatment group and 128 subjects in the placebo group will provide 85% power based on an MMRM model using simulation method. The simulation assumed a correlation of 0.7 between the repeated measures, and a common dropout rate of 14%, based on historical data of escitalopram in pediatric subjects.

SAP SCT-MD-60 Allergan

Page 41 of 53

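### Binary endpoints: treatment-by-age and treatment-by-sex terms are listed with no rule for keeping them and no stated Week 8 contrast, and the only fallback is an LOCF logistic model without the stratification factors

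*SAP*

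**What the plan says.** SAP 9.2.1 plans a pseudo-likelihood repeated-measures logistic model for PARS response. Besides treatment, age group, sex and visit, it names "treatment-by-age group interaction, treatment-by-sex interaction, treatment by visit interaction, treatment-by-age group-by-sex interaction, and baseline score as a covariate". Protocol 11.5.1.2 has the same list: "treatment-by-age group interaction, treatment-by-sex interaction, treatment-by-visit interaction, and treatment-by-age group-by-sex interaction", plus baseline score. Both documents put these terms forward for consideration in the modelling. Neither gives a rule for keeping or dropping them, and neither states the Week 8 treatment contrast or the weights given to the strata.

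SAP 9.2.2, 9.2.4 and 9.2.6 apply the same method to remission on the PARS, CGI-S and CGAS, so four endpoints are covered.

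If the model does not converge, SAP 9.2.1 has one further step: "a logistic regression model with treatment group and baseline score as explanatory variables will be used", with LOCF for missing post-baseline data.

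The primary MMRM (SAP 9.1.2) has age group and sex as main effects next to "pooled study center, visit, and treatment group-by-visit interaction as the fixed effects". It has no treatment-by-age or treatment-by-sex term, and it has an ordered list of simpler covariance structures to try on non-convergence. Randomisation is stratified by age group and sex (SAP 3.0, protocol 8.4.4). For the secondary endpoints, SAP 9.2 says: "Inferential testing for the secondary endpoints will be reported with nominal p-values".

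**The concern.** With all listed terms in the model, each arm has four freely fitted age-by-sex cells. The three-way class effect also absorbs age-by-sex, which is not listed separately. No single treatment effect then exists until the cells are weighted, and the plan does not say how. Software defaults for least-squares means weight them equally, so the smallest cell counts as much as the largest. That costs precision when strata are unequal. If effects differ by stratum, it also moves the estimate away from what a model without these terms, such as the primary one, would give.

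The second issue is convergence. Treatment-by-stratum cells are where an uncommon outcome is most likely to have no events. The plan has no step that removes those terms first. It goes directly to a model that gives up the repeated-measures structure and both stratification factors and brings in LOCF. Four parallel endpoints could end up with different models and missing-data rules because of chance sparse cells.

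**Working it through.** **1. The plan's own power figure.** It concerns the primary endpoint only. Inputs (SAP 14.0): "treatment group difference of 2.30 units relative to pooled standard deviation of 5.79"; "a sample size of 128 subjects in the escitalopram treatment group and 128 subjects in the placebo group will provide 85% power"; correlation 0.7; dropout 14%. The test is made "using a 2-sided α of 0.05" (SAP 9.1.2). Effect size = 2.30/5.79 = 0.397. A two-sample calculation gives 88.8% at 128 per arm, 85.4% at the 115 evaluable per arm of protocol 8.3.1, and 83.8% at 128 × 0.86 = 110. A two-visit likelihood simulation with correlation 0.7 and 14% dropout gives 86.1%. The stated 85% is reproduced to within about 2 points. No power is stated for any binary endpoint.

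**2. Cost of equal weighting.** Let p_s be the share of stratum s. At a common event rate, the variance of an equal-weighted contrast relative to a share-weighted one is (1/16) × Σ(1/p_s). If age and sex are independent, with adolescent share a and female share f, this equals 1/[16·a(1−a)·f(1−f)]. The documents give no shares, so these are assumptions. The last column shows what a test with 85% power would become: Φ((1.96 + 1.036)/√inflation − 1.96).

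| Adolescent / female | 16·a(1−a)·f(1−f) | Inflation | Smallest cell of 115 | 85% becomes |
|---|---|---|---|---|
| 50 / 50% | 1.000 | 1.00 | 29 | 85.0% |
| 60 / 60% | 0.922 | 1.09 | 18 | 82.0% |
| 65 / 60% | 0.874 | 1.15 | 16 | 80.0% |
| 70 / 60% | 0.806 | 1.24 | 14 | 76.8% |
| 75 / 60% | 0.720 | 1.39 | 12 | 72.0% |
| 75 / 65% | 0.683 | 1.47 | 10 | 69.7% |

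**3. Simulated Week 8 power and separation.** The model was a two-visit (Weeks 2 and 8) marginal logistic regression with sandwich standard errors: 119 per arm, about 110 observed at Week 8, Week 2 rates 35% of Week 8, the same effect in every stratum, no baseline covariate, 2,000 trials per setting. Each cell shows power with main effects plus treatment-by-visit, then power with the SAP's terms (among fits without separation), then the share of trials with separation under the SAP's terms.

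| Placebo / active rate | 50 / 50% strata | 65 / 60% strata | 75 / 65% strata |
|---|---|---|---|
| 30 / 48% | 79.7, 79.7; 0% | 78.6, 73.3; 0.2% | 79.0, 63.7; 3% |
| 15 / 29% | 71.2, 70.5; 2% | 69.9, 63.4; 8% | 70.9, 52.1; 22% |
| 8 / 18% | 57.0, 51.0; 25% | 57.6, 43.2; 39% | 56.0, 33.1; 59% |

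The losses at 65/60 strata are 5.3, 6.5 and 14.4 points. The formula in step 2 explains the first: Φ((1.96 + 0.793)/√1.145 − 1.96) = 73.0%, against 73.3% simulated. For the rarest outcome it predicts only 52.0%, against 43.2%; the rest is sparse-cell loss.

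**4. CGAS.** CGAS is rated at five post-baseline visits, and the age and sex interactions are not crossed with visit, so a cell is empty only if it has no event at any visit. A separate simulation assumed 115 per arm, latent correlation 0.7, odds ratio 2.1, 60% female and low early-visit rates. At 12% placebo remission and 30% children, the chance of an empty cell falls from about 42% (Week 8 alone) to 11–12% with five visits. At 8% and 25% children it falls from about 76% to 36–39%. With the two visits of PARS and CGI-S the fall is small: 41% to 31%, and 77% to 67%.

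**5. When the estimate moves.** Assume log-odds effects of 0.2 in children and 0.8 in adolescents, with 65% adolescents. Share-weighted: 0.35 × 0.2 + 0.65 × 0.8 = 0.59. Equal-weighted: 0.50. With equal effects or equal strata the two agree.

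**The case against.** A reader might infer that the plan fixes these interactions in the model and averages the strata equally. The documents do not support that. The terms are only candidates, least-squares means are named for the primary analysis and not for the binary model, and observed-margin weights would avoid the problem. So the variance cost is conditional. What stands is that the plan leaves both choices open.

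A reader might also infer that the primary and responder results necessarily describe differently weighted populations. As step 5 shows, that needs unequal strata and unequal effects together.

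A third tempting inference is that an empty cell makes the model fail. The trigger in SAP 9.2.1 is non-convergence. Separation is only a proxy for it, and the simulations did not use GLIMMIX pseudo-likelihood. The concern is also weaker for CGAS.

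Removing the interactions does not close the LOCF route. Treatment-by-visit can itself separate when an arm has no remitters at an early visit: in the five-visit simulation, in 9–32% of trials at a 12% placebo rate and 21–51% at 8%. This stands, and it is why steps before LOCF are needed as well. The fallback's omission of age and sex is likewise a separate gap, not a result of the interactions.

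Finally, the primary objective names children and adolescents, and the SAP plans no efficacy subgroup analysis by age or sex. These terms are its only listed look at effect modification. That is a reason to move them to a separate output, not to delete them.

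**Conclusion.** The point holds as a gap in specification with a conditional cost. If the listed terms are kept and default weights are used, variance inflation runs from 1.00 with equal strata to 1.39 with 60% female and 25% children. Power loss is near zero with balanced strata and common events, about 5 to 7 points at 65% adolescents and 60% female with Week 8 placebo rates of 15% or more, and greater beyond that. Every share and rate here is assumed. For uncommon remission outcomes, sparse cells raise the chance of the LOCF fallback, by an amount the documents do not allow one to fix.

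The affected endpoints are secondary, with nominal p-values, no multiplicity adjustment and no stated power. No figure in the plan is broken, and the primary analysis is untouched.

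**What to change.** - Prespecify treatment, age group, sex, visit, treatment-by-visit and baseline score as the model for the treatment comparison on all four endpoints.
- State the Week 8 contrast that gives the treatment effect.
- Put simplification steps before the LOCF fallback, as the primary MMRM already has for its covariance structure.
- Keep age group and sex in the fallback logistic model.
- Report effect modification by age and sex as a separate exploratory analysis.
- Amend protocol 11.5.1.2 to match, or record the change in SAP 17.0. The logistic/LOCF fallback is itself absent from protocol 11.5.1.2, and SAP 17.0 does not mention it.

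Keeping the stratification factors in the fallback is a free improvement. Moving the interactions is a cheap one: the small downside is one extra analysis. The rest is wording, with no effect on data collection or sample size.
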